7.4.2. Pharmacokinetic Criteria for Adjustment or Stopping Doses

There are no pre-defined Pharmacokinetic criteria for adjusting or stopping doses. Subject termination will be governed by safety, tolerability and Investigator discretion.

7.5. Criteria for Study Termination

SK Life Science, Inc. (SKLSI) may terminate the study at any time. For reasonable cause, either the Investigator or the IRB may terminate the study as well. Conditions that may warrant termination include, but are not limited to:

- subject or investigator noncompliance,
- unsatisfactory subject enrollment,
- lack of adherence to protocol procedures,
- lack of evaluable and/or complete data,
- potentially unacceptable risk to study subjects,
- decision to modify drug development plan,
- decision by the FDA or other regulatory authority.

Written notification that includes the reason for the protocol termination is required.

8. SELECTION AND WITHDRAWAL OF SUBJECTS

Healthy subjects who meet all the inclusion criteria and none of the exclusion criteria will be eligible for participation in this study. The study population will consist of a balanced representation of genders and ethnic groups to the extent possible.

Adherence to the study design requirements, including those specified in the schedule of assessments ([Table 4](#)), is essential and required for study conduct. Continued eligibility will be assessed upon entry into the clinic prior to the start of each visit.

All screening evaluations must be completed and reviewed to confirm that potential subjects meet all eligibility criteria. The subject's selected by the clinical site will be reviewed by SKLSI for final approval. The investigator will maintain a screening log in order to record details of all screened subjects and to confirm eligibility or record reasons for screening failure, as applicable.

Subjects may be re-screened only once within an appropriate time window in case of out of range results.

8.1. Subject Inclusion Criteria

3. Male or female subjects of 18 to 50 years of age (inclusive), at the time of screening
4. Able to read, understand, sign, and date a written informed consent form (ICF) before study participation at screening
5. Agree to use effective methods of contraception as described in Section [12.1.7.8](#) and Section [12.1.7.9](#).
6. Body mass index (BMI) between 18.5 and 30.0 kg/m² (inclusive) at screening
7. Judged to be in good health on the basis of medical history, physical examination, and routine laboratory measurements (i.e., without clinically relevant pathology)
8. Electrocardiogram (ECG) (12-lead), arterial blood pressure, and heart rate within the normal range of the study center or considered not clinically significant by the Investigator.
9. Able to understand and comply with protocol requirements and instructions and likely to complete the study as planned
10. Females of non-childbearing potential (18 to 50 years of age (inclusive)), who have undergone a sterilization procedure at least 6 months prior to dosing with official documentation (e.g., bilateral tubal ligation or bilateral salpingectomy or hysterectomy), or be postmenopausal with amenorrhea for at least 1 year prior to dosing and follicle-stimulating hormone (FSH) serum levels consistent with postmenopausal status as per Principal Investigator's judgment

8.2. Subject Exclusion Criteria

1. Clinically relevant abnormal medical history, abnormal findings on physical examination, vital signs, ECG, or laboratory tests at Screening that the Investigator judges as likely to interfere with the objectives of the trial or the safety of the volunteer

2. Smokers (subjects who have smoked within 6 months at screening)
3. History of any drug related hypersensitivity reactions as well as severe hypersensitivity reactions (like angioedema) or DRESS as evaluated by the Investigator
4. Cholecystectomy and/or surgery of the gastrointestinal tract that could interfere with pharmacokinetics of the study drug (except appendectomy and simple hernia repair)
5. Any prescribed or over-the-counter medication taken within 2 weeks prior to start of administration of study drug (Day 1) or within 6 times the elimination half-life of the medication prior to start of study drug intake (whichever is longer). Occasional use of acetaminophen is allowed up until 24 hours before dosing
6. Consumption of herbal medications, dietary supplements and specific fruit products. Subjects should have stopped consumption of herbal medications or dietary supplements (e.g., St. John's Wort, ginkgo biloba, and garlic supplements), and grapefruit or grapefruit juice, or Seville oranges at least 2 weeks before the first dosing day of study drug. Vitamins/mineral supplements are allowed up until 24 hours before dosing
7. History of drug or alcohol abuse or addiction within 2 years before the start of study drug dosing, or a positive test results for alcohol or drugs of abuse, such as amphetamine, barbiturate, benzodiazepine, cocaine, methadone, opiates, oxycodone, phencyclidine, propoxyphene, cannabinoid (THC), MDMA (Ecstasy), methaqualone, and tricyclic antidepressant (TCA)
8. Regular consumption of more than 2 units of alcoholic beverages per day or more than 14 units per week (1 unit of alcohol equals 1 pint [473 mL] of beer or lager, 1 glass [125 mL] of wine, 25 mL shot of 40% spirit) before screening
9. Consumption of an average of more than 5 servings (8 ounces per serving) per day of coffee, cola, or other caffeinated or methyl xanthine beverages before screening
10. Consumption of any caffeine- or methyl xanthine-containing products (e.g., coffee, tea, chocolate, or soda) or alcoholic beverages within 48 hours prior to Day 1 of each period and until the end of each PK sampling period
11. Participation in a clinical study involving administration of either an investigational or a marketed drug within 2 months or 7 half-lives (whichever is longer) before screening
12. Blood donation or a significant loss of blood within 60 days of the start of study drug dosing or donation of more than 1 unit of plasma within 7 days before screening
13. Positive result at screening for any of the following infectious disease tests: hepatitis B surface antigen (HBsAg), hepatitis C virus antibody (HCV Ab), human immunodeficiency virus antigen and antibody (HIV Ag, HIV Ab)
14. Illness within 5 days before the start of study drug dosing ("illness" is defined as an acute [serious or non-serious] condition [e.g., the flu or the common cold])
15. History of any known relevant allergy/hypersensitivity (including allergy to the trial medication or its excipients)
16. Subject who is judged not eligible for study participation by Investigator

17. History of Familial Short QT syndrome.

8.3. Subject Withdrawal Criteria

Any subject may be withdrawn from the study at the discretion of the Investigator. The subject is also free to terminate his/her participation at any time. However, if the subject has been dosed with study medication, it is recommended to ask the subject to remain in contact with the center, and the investigational site should make every effort to convince the subject to return for a safety follow-up visit. The Investigator will also undertake to obtain more detailed information about any subject lost to follow-up. Subjects withdrawn from the study must not be re-included.

8.3.1. Withdrawn Subject Data Collection

The principal Investigator and/or designee will document on the termination page of the CRF and in the subject's medical records the primary reason for the subject's withdrawal as follows:

- Lost to follow-up: subjects who leave the clinic during the hospitalization period or do not attend the following visit. Intensive efforts should be made to locate and recall them if possible and, at a minimum, to determine their health status;
- AE: an AE form must be completed; the type of AE should be specified;
- Deviation from protocol;
- Consent withdrawn;
- Other: if none of the above-mentioned reasons are applicable, then the reason will be specified.

All withdrawals will be reported immediately to SKLSI. For all dropouts, a Follow-up visit will be arranged for approximately 21 days after the most recent drug administration and will document the progress of their condition. In every case, the CRF must be filled in up to the last visit performed.

8.3.2. Lost to Follow-Up

A subject will be considered lost to follow-up if he or she fails to return for scheduled visits and is unable to be contacted by the study site. The following actions must be taken if a subject fails to return to the clinic for a required study visit:

- The site must attempt to contact the subject and reschedule the missed visit as soon as possible, counsel the subject on the importance of maintaining the assigned visit schedule and ascertain whether or not the subject wishes to and/or should continue in the study;
- In cases in which the subject is deemed lost to follow-up, the Investigator or designee must make every effort to regain contact with the subject (where possible, 3 telephone calls and, if necessary, a certified letter to the subject's last known mailing address or local equivalent methods). These contact attempts should be documented in the subject's medical record;

- Should the subject continue to be unreachable, he/she will be considered to have withdrawn from the study with a primary reason of lost to Follow-up.

8.3.3. Replacement of Subjects

Subjects who withdraw or are withdrawn during the study for reasons unrelated to safety may be replaced in order to have at least 20 evaluable subjects who completed the 3 treatment periods. In case of replacement, a subject will be assigned to the same treatment sequence as the discontinued subject.

In case of moderate or severe AE causing the subject to withdraw, a joint decision between SKLSI and the Investigator will be taken on the appropriateness of replacing the subject.

9. TREATMENT OF SUBJECTS

9.1. Description of Study Drug

Table 5 lists the details of the two cenobamate formulations to be used in this study.

Table 5: Investigational Product

Investigational Product		
Product Name:	Cenobamate	Cenobamate
Activity:	Reducer of repetitive neuronal firing by enhancing the fast and slow inactivation of sodium channels and by inhibiting the persistent component of the sodium current. A positive allosteric modulator of six subtypes of the γ -aminobutyric acid (GABA A) ion channel.	
Dosage Form:	Tablet	Liquid Suspension
Strength:	200 mg	10 mg/mL
Route of Administration	Oral	Oral
Dosage Form	Film-coated oval (9.5 mm by 20 mm) light orange tablets	Suspension
Manufacturer	Patheon for SK Life Science, Inc	Manufactured by CoreRx, Florida, USA for SK Life Science, Inc

9.2. Concomitant Medications

The use of any investigational drug is prohibited within 30 days before the first administration of cenobamate. The use of any prescription or over-the-counter drug (other than hormonal contraceptives for women of childbearing potential) is prohibited within less than 15 days before the first administration of cenobamate, with the exception of vitamin/mineral supplements and the occasional use of acetaminophen, which is allowed up to 24 hours before dosing in any treatment period.

For any subject, if the use of any concomitant treatment becomes necessary (e.g., for the treatment of an AE), the treatment must be recorded in the CRF, including the reason for treatment, generic name of the drug, dosage, route, and date and time of administration. If a treatment is administered, SKLSI's medical monitor must be promptly notified in order to assess the subject's eligibility for continuing study participation.

9.2.1. Prior Treatments

Reasonable efforts will be made to determine all relevant treatments received by the subject within 3 months before the first administration of cenobamate (within 15 days before the first administration of cenobamate for over-the-counter drugs).

The use of any prescription or over-the-counter drugs (other than hormonal contraceptives for women of childbearing potential) as well as herbal medications, dietary supplements and specific

fruit products is prohibited within 2 weeks before the first administration of cenobamate, with the exception of vitamin/mineral supplements and the occasional use of acetaminophen, which are allowed up to 24 hours before dosing.

All relevant information must be recorded on the subject's CRF.

9.3. Treatment Compliance

The following measures will be employed to ensure treatment compliance:

- All study drug administrations will be under the supervision of the Investigator or designee;
- A mouth and hand check for drug product will be carried out for each subject after dosing to ensure that all of the dose has been swallowed.

Subjects who are unable to adhere to the above measures may be removed from the study based on the SKLSI's decision (on a case-by-case basis) and the CRF will be documented accordingly.

9.3.1. Lifestyle Guidelines

9.3.1.1. Meals and Dietary Restrictions

Subjects will need to stop consuming grapefruit or drink grapefruit-containing products, or Seville oranges at least 2 weeks before the first dosing day of study drug. Vitamins/mineral supplements are allowed up until 24 hours before dosing, as specified in exclusion criteria (Section 8.2).

9.3.1.1.1. Treatment A and Treatment B Meals and Dietary Restrictions

On days that a subject will be confined to the CRU for Treatment A and/or Treatment B, an overnight fast will be imposed (when needed) so that no food is consumed within at least 10 hours before cenobamate administration. On days that a subject will be confined to the CRU, dinner will be served the day prior to dosing (Day -1, Day 21, or Day 42) ending at least 10 hours before dosing. The next meal will be a lunch approximately 4 hours after dosing the following day followed by a dinner approximately 10 hours after dosing. On subsequent days of confinement, a breakfast, lunch and dinner will be provided at appropriate times.

9.3.1.1.2. Treatment C Meals and Dietary Restrictions

On days that a subject will be confined to the CRU for Treatment C, dinner will be served the day prior to dosing (Day -1, Day 21, or Day 42) approximately 10 hours prior to dosing. On the day of dosing (Day 1, Day 22, or Day 43) a high-calorie, high-fat breakfast will be provided approximately 30 mins prior to dosing. The breakfast should be consumed with 30 minutes or less and Treatment C should be approximately 30 mins after the start of a meal (Section 10.5.2).

9.3.1.2. Alcohol, Caffeine, and Tobacco

Alcohol, caffeine, and tobacco restrictions are specified in exclusion criteria (Section 8.2). Subjects may undergo an alcohol test at the discretion of the Investigator.

9.3.1.3. Physical Activity

Subjects will abstain from strenuous exercise (e.g., heavy lifting, weight training or aerobics) for at least 48 hours prior to each blood collection for clinical laboratory tests. Walking at a normal pace will be permitted.

9.4. Randomization and Blinding

This study is an open-label study.

Prior to dosing on Day 1, subjects will be randomized to receive one of six treatment sequences as outlined in [Table 3](#). The randomization list will be generated by the statistician responsible for this study using SAS® software. One copy of the randomization list will be provided to the pharmacist for preparation of the appropriate treatment.

10. STUDY DRUG MATERIALS AND MANAGEMENT

10.1. Study Drug

10.1.1. Cenobamate Oral Tablet

The cenobamate oral tablet formulation is an Opadry® II light orange film coated tablet with the following inactive excipients: microcrystalline cellulose, lactose monohydrate, sodium starch glycolate, colloidal silicon dioxide, and magnesium stearate.

10.1.2. Cenobamate Oral Suspension

The cenobamate oral suspension formulation is manufactured from commonly used inactive ingredients, suitable flavor, preservative and sweetener.

10.2. Study Drug Packaging and Labeling

Packaging and labelling will be done in accordance with the Rules Governing Medicinal Products in the European Union, Volume 4: Good Manufacturing Practice (GMP). The Study drug (investigational medicinal product) labels will include all the information required by Annex 13 to GMP.

The 200 mg tablets are packaged in High Density Polyethylene (HDPE) bottles with Polypropylene (PP) CRC cap.

For oral suspension, contents are packed in amber glass bottle with CRC cap. A Push in Bottle Adapter (PIBA) suitable for the packaged bottle will be provided. The study site will obtain oral syringes of suitable capacity for dosing the oral suspension formulation of cenobamate.

SKLSI will ship a sufficient supply of cenobamate (either oral tablet formulation or oral suspension formulation) to the study site.

10.3. Study Drug Storage

At the study site, study drug must be kept in a secure, locked area or locked cabinet with access restricted to designated study site personnel. Study drug will be stored upright at room temperature in a dry area, protected from light, monitored for temperature.

10.4. Study Drug Preparation

The appropriate dose and formulation of cenobamate will be prepared and dispensed by a pharmacist at the clinical site.

Before beginning the dispensing process, the pharmacy staff will read and understand the study protocol and accompanying study treatment preparation, dispensing, and administration instructions (if applicable). Only eligible subjects participating in the study will receive the study drugs. Only authorized research site staff may supply or administer the study drugs. Any questions related to dispensing of the study drugs will be resolved prior to the start of the study by communication with an SKLSI representative. Additional study drug preparation will be followed as per the pharmacy manual.

10.5. Administration

Study drug will be administered orally in either tablet or suspension formulation.

10.5.1. Timing of Doses in the Study

10.5.1.1. Timing of Doses for Treatment A and Treatment B

- The study drug will be orally administered to subjects in the morning after a 10-hour overnight fast (no food or beverages allowed except for tap water).
- The study drug will be swallowed together with 240 mL tap water (room temperature). The study drug should be swallowed whole and should not be chewed.
- Administration of the study drug will be supervised by the Investigator or designee. After drug administration, a mouth and hand inspection will take place.
- Fasting will continue until approximately 4 hours post-dose when lunch will be served.
- Subjects will also be instructed not to drink fluids over a period extending from 2 hours prior to 2 hours after study drug administration, except water used for study drug administration.
- A dinner will be provided approximately 10 hours after dosing.

10.5.1.2. Timing of Doses for Treatment C

- The study drug will be orally administered to subjects in the morning approximately 30 minutes after the start of a high-calorie, high-fat meal.
- The study drug will be swallowed together with 240 mL tap water (room temperature). The study drug should be swallowed whole.
- Administration of the study drug will be supervised by the Investigator or designee. After drug administration, a mouth and hand inspection will take place.
- A lunch and dinner will be served approximately 4 hours and 10 hours post-dose, respectively.

10.5.2. High-Calorie, High-Fat Meal for Treatment C

Subjects that are taking the oral suspension formulation under fed conditions (Treatment C) will be given a high-calorie (approximately 800 – 1000 calories) and high-fat (approximately 50% of total caloric content of the meal) meal as recommended by the FDA.⁴ This meal should derive approximately 150, 250, and 500 – 600 calories from protein, carbohydrate, and fat, respectively. For instance, the breakfast can contain 2 eggs fried in butter, 2 strips of bacon, 2 slices of toast with butter, 4 ounces of hash brown potatoes and 8 ounces of whole milk. Substitutions in this test breakfast can be made provided that the meal provides a similar amount of calories from protein, carbohydrate, and fat and has comparable meal volume and viscosity. The final composition of the breakfast will be reported in the clinical study report.

Subjects receiving the high calorie, high-fat breakfast will need to adhere to the following schedule:

- The meal will be taken about 30 minutes prior to the administration of cenobamate,
- The meal should be eaten within 30 minutes or less,
- Cenobamate will be administered approximately 30 minutes after the start of the meal.

Water will be allowed ad libitum except for one hour before and after cenobamate administration, with the exception of the 240 mL of water taken with each dose.

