The study drug will be administered in the morning of Day 1, Day 22, and Day 43 for Period 1, Period 2, and Period 3, respectively. Study drug will be administered after all pre-dose assessments have been completed. The subjects will stay at the clinical site until Day 4, Day 25, and Day 46 for Period 1, Period 2, and Period 3, respectively. The subjects will be discharged after completion of all scheduled assessments. Outpatient visits will be performed as outlined in [Table 4](#).

Follow-up:

A follow-up visit will be performed on Day 69 (± 1 day)

Refer to the Schedule of Assessments ([Table 4](#)) for further details.

Reference therapy, dosage and mode of administration:

Treatment A: Oral Dose of cenobamate administered as a single 200 mg tablet on Day 1 under fasted conditions

Treatment B: Oral Dose of cenobamate administered as a single 200 mg/20 mL suspension on Day 1 under fasted conditions

Treatment C: Oral Dose of cenobamate administered as a single 200 mg/20 mL suspension on Day 1 under fed conditions

Evaluation:**Pharmacokinetics:**

Serial blood samples for PK assessments will be sampled at various time points from Day 1, Day 22, and Day 43 starting at pre-dose through 456 hours (20 days) following oral administration of cenobamate tablets or suspension (See [Table 4](#)).

The PK samples may be used for additional exploratory PK and/or metabolite analyses.

Descriptive statistics and graphs will be generated for plasma concentrations and PK parameters for each treatment.

The formulation effect will be tested for: Cenobamate oral suspension administered under fed and fasting conditions and cenobamate oral tablet administered under fasting conditions. These analyses will be conducted separately on C_{max} , AUClast and AUC_{∞} using a mixed model on the log transformed data with treatment, sequence and period as fixed effects and subject within sequence as random effect. Geometric mean ratios (GMRs) will be computed for:

1. Cenobamate oral suspension administered under fasted conditions versus cenobamate oral tablet administered under fasting conditions
2. Cenobamate oral suspension administered under fed conditions versus cenobamate oral suspension administered under fasting conditions

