13.1.3.2. Formulation and Food Effect Analysis

An analysis of variance (ANOVA) will be used to compare suspension vs. tablet formulations and suspension under fed vs. suspension under fasted conditions. PK parameter (C_{\max} , AUC_{last} , and AUC_{∞}) values will be log-transformed for all subjects included in the PK population set and the ratio and corresponding 90% CIs for the ratio of the test (suspension or fed) vs. reference (tablet or fasted) will be compared. An absence of effect will be concluded if the 90% CIs lie within the 80% - 125% predefined boundaries.

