5.3 Meal Record

Details of meal records, such as meal type, date/time of meal, and amount consumed will be listed.

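### The protocol gives two water rules around dosing: read by heading, permitted water differs between the fed and fasted suspension arms; read as general, the rules contradict each other

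*Protocol*

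**What the plan says.** Protocol 10.5.1.1, for Treatments A and B: "Subjects will also be instructed not to drink fluids over a period extending from 2 hours prior to 2 hours after study drug administration", with the dosing water as the only exception. The same section permits tap water during the overnight fast, so for these treatments the bar on water covers the 4 h around the dose.

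Protocol 10.5.1.2, for Treatment C, covers the meal, the dosing water and later meals. It sets no fluid restriction.

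Protocol 10.5.2, headed for the Treatment C meal, closes with: "Water will be allowed ad libitum except for one hour before and after cenobamate administration". It exempts the 240 mL of water and ties that water to each dose, not to the Treatment C dose in particular.

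Dosing water is 240 mL for all three treatments. The example test breakfast includes "4 ounces of hash brown potatoes and 8 ounces of whole milk".

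The second primary comparison (Protocol Synopsis; SAP 4.6.3) is "Cenobamate oral suspension administered under fed conditions versus cenobamate oral suspension administered under fasting conditions". The decision rule in Protocol 13.1.3.2 is "An absence of effect will be concluded if the 90% CIs lie within the 80% - 125% predefined boundaries".

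On intake data, SAP 5.3 says: "Details of meal records, such as meal type, date/time of meal, and amount consumed will be listed". It names no record of water.

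**The concern.** The C/B ratio will be read as the effect of food on the suspension, and Protocol 5.3.1 says that the result will guide use of the suspension in paediatric studies. The protocol otherwise keeps the two arms alike: the same 200 mg suspension dose, the same dosing water, and the same approximate lunch and dinner times. A different rule on free water is a second difference between the arms. The fed state does not require it, and the protocol gives no reason for it.

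If the rule does differ by treatment, it follows treatment exactly: every C dose falls under one rule and every B dose under the other. Randomisation, the period and sequence terms and the random subject effect cannot separate it from food. Because the water is ad libitum, its volume is not standardised either.

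If the sentence in 10.5.2 was instead meant for every dose, site staff have two incompatible instructions for the same fasted dosing morning.

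**Working it through.** **Step 1: the rules side by side** (times relative to dosing; dosing water excluded).

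| Interval | A and B (10.5.1.1) | C (10.5.2, read by heading) |
|---|---|---|
| -2 to -1 h | no fluids | water free |
| -1 to 0 h | no fluids | no water; test meal from about -30 min |
| 0 to +1 h | no fluids | no water |
| +1 to +2 h | no fluids | water free |

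The window is 2 + 2 = 4 h for A and B, and 1 + 1 = 2 h for C. Permitted water differs for 4 - 2 = 2 h in total: one hour before the dose and one hour after it.

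**Step 2: does another section resolve it?** No. Section 10.5.1.2 is silent. The meal and diet sections under 9.3.1.1 give meal times and dietary restrictions but no rule on water around dosing.

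**Step 3: which contrasts are touched?** B versus A (primary objective 1): both treatments follow 10.5.1.1, so under the reading by heading this contrast is unaffected. C versus B (primary objective 2): the rules differ. SAP 4.6.3 estimates C minus B directly from the treatment effect, so the water rule is fully aliased with food.

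**Step 4: scale.** The documents give no water effect, so no bias can be computed. What can be computed is how large a shift would have to be to matter for the decision rule. The inputs are 24 completers (Protocol 7.2) and within-subject CVs of 14% for Cmax and 5% for AUC, the upper end of the 4-5% in Protocol 5.1.2.1.

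- Error df for three periods: 72 - 1 - 23 - 2 - 2 = 44.
- Half-width on the log scale = t(0.95, 44) × sqrt(ln(1 + CV²)) × sqrt(2/24), with t = 1.680.
- Cmax: 1.680 × 0.1393 × 0.2887 = 0.0676.
- AUC: 1.680 × 0.0500 × 0.2887 = 0.0242.
- Shift from a true ratio of 1 at which the expected upper limit reaches 1.25 (ln 1.25 = 0.2231): Cmax exp(0.2231 - 0.0676) = 1.17; AUC exp(0.2231 - 0.0242) = 1.22.
- Illustration with an assumed 3% shift, which has no source in the documents. Upward, the upper limit is exp(0.0296 + 0.0676) = 1.10 for Cmax and exp(0.0296 + 0.0242) = 1.06 for AUC. Downward, the lower limit is exp(-0.0305 - 0.0676) = 0.91 for Cmax and exp(-0.0305 - 0.0242) = 0.95 for AUC. All are inside 0.80 to 1.25.

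**The case against.** **Permission is not intake.** A reader might infer that water intake differs between the arms. The documents show only that Treatment C subjects may drink in two extra hours, not that they will or how much. This stands, and the point is about permitted water.

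**Timing.** A reader might infer that the whole difference falls during absorption. One of the two hours is before the dose. Only +1 to +2 h is after it. That hour lies within the 1 to 4 h range for the peak in Protocol 5.1.2.1, but the range comes from earlier studies, and Protocol 5.3.2.2 calls the disposition of an oral liquid unknown. Nothing in the documents links water in that hour to a change in exposure, least of all in AUC, which is sampled to 456 h. This stands.

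**Precision.** A reader might set a shift of 2-3% beside the AUC half-width of 0.0242 and infer a material problem. The documents supply no such shift, and the relevant yardstick is the 80% to 125% rule, which a shift of that size would not threaten when the true ratio is near 1.

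**Fluid would differ anyway.** The milk in the example breakfast falls inside the no-fluid window for Treatment B. That is true, but the meal beverage belongs to the fed condition and free water does not. A common rule would make the contrast cleaner, not free of every fluid difference.

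**The rule may be general.** The reference to each dose allows 10.5.2 to be read as covering all treatments. In that case no difference between arms was intended. This also stands, but it exchanges an unexplained difference for a direct contradiction with 10.5.1.1.

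**Conclusion.** The fluid rules in 10.5.1.1 and 10.5.2 do not match, and no section reconciles them. Read by heading, C and B differ in permitted water for 2 h in total, and the planned analysis cannot separate that from food. Read as general, the two sections contradict each other. Either way the text needs correction.

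The consequence is modest. No bias can be computed, because the documents give neither an effect of water nor data on intake. Assuming 24 completers, the protocol's CVs and a true ratio near 1, a small shift is unlikely to change the 80% to 125% conclusion, although it would enter the reported C/B ratio. The documents do not support a claim that the food-effect conclusion is biased, or that the sponsor chose the difference deliberately. The formulation comparison is not affected by the difference between arms. This is a free improvement and does not put the design in doubt.

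**What to change.** Reconcile 10.5.1.1, 10.5.1.2 and 10.5.2 so that one fluid-restriction window applies to Treatments A, B and C, with the dosing water and the test-meal beverage as the only exceptions. State the same rule in all three sections, and say whether it covers all fluids or water only, since 10.5.1.1 refers to fluids and 10.5.2 to water. The length of the window is for the sponsor to choose.

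The cost is protocol wording. It needs no new procedure, visit, sample or data field, and no change to the statistical model.
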